Study Design	
This is a multicenter, prospective, randomized, double-blind, sham-controlled, parallel-design study conducted in the United States.
 
The pivotal study cohort will consist of 270 pre-planned study subjects which will be randomized in 2:1 ratio to the Treatment or the Control group from up to 12 sites. Subjects who sign the informed consent and are deemed eligible following a general and endoscopic screening will be enrolled in the study and randomized.
 
Subjects assigned to the Treatment group will receive the TPS placement and the subjects in the Control group will undergo a sham procedure without TPS placement. The subjects will be blinded to their treatment. The Investigators and/or study coordinators who collect the primary outcome data will be masked to subjects' treatments.
 
Subjects will be followed for 12 months or less than 12 months if the subject achieves the midpoint of the normal BMI range (22 kg/m²), at which time the subject is considered to have completed the study and the device removed if the subject had received the TPS device.
 
Subjects will receive brief (15 minute) lifestyle-modification counseling sessions at each follow up visit. They also will receive brief (15min) telephone calls in the months that do not include in person visits between 6 and 12 months (in months 7, 8, 10, and 11). These counseling sessions are centrally designed to improve adherence to recommendations to consume a healthy diet and increase physical activity to promote weight loss and overall health. The counseling sessions and telephone calls will be provided by a member of the research team (dietitian, nurse, etc.) trained in the delivery of the prescribed lifestyle counseling.

Patient Population	Male and female subjects, 22-60 years of age, with a BMI of 35.0 to 40.0 kg/m ² , inclusive, or a BMI of 30.0 to 34.9 kg/m ² with at least one obesity-related comorbidity.

Co-Primary Endpoints
	
 • Mean percent total body weight loss (% TBL) between the Treatment and the Control group at 12 months after the index procedure. • The proportion of subjects in the Treatment group who achieve $\geq 5\%$ TBL at 12 months after the index procedure.

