
Secondary Endpoints
	
 • Proportion of subjects who achieve at least 7% and 10% TBL at 12 months in the Treatment versus Control group • Percent total body weight loss over 12 months in the Treatment versus Control group • Percent excess weight loss over 12 months in the Treatment versus Control group • Proportion of subjects who achieve at least one obesity class reduction at 12 months in the Treatment versus Control group • Change of BMI over 12 months from baseline in the Treatment group • Change in weight-related quality of life over 12 months as assessed by IWQOL-Lite Questionnaire • Change in eating behavior over 12 months as assessed by the Eating Inventory • Change in appetite, hunger and fullness over 12 months as assessed by Visual Analog Scales • Change in comorbid conditions over 12 months in the Treatment group: 
 ○ Prevalence of the metabolic syndrome and its individual components ○ Glucose, insulin, and insulin resistance (as estimated by HOMA) ○ High sensitivity C-reactive protein (hsCRP) ○ Lipid levels (LDL-C, HDL-C, and triglycerides) ○ Blood pressure ○ Waist circumference

Safety Evaluation
	
Safety will be characterized through a summary of the incidence of adverse events. A Clinical Event Committee (CEC) will review and adjudicate all serious device-related adverse events and any other events deemed necessary.

Key Inclusion Criteria
	
 1. Male and female subjects between the ages of 22 to 60 2. A BMI between 30.0 to 40.0 kg/m² inclusive. Subjects with a BMI of 30.0 kg/m² to 34.9 kg/m² are required to have one or more of the following obesity-related mild-moderate comorbidities: 
 a. Type 2 Diabetes: meet one of the following criteria and currently not using insulin 
 i. HbA1c 6.5%-7.5% ii. Controlled, on stable dose of oral medications for at least 3 months b. Hypertension, meet one of the following criteria: 
 i. Arterial blood pressure >140 mmHg systolic or >90 mmHg diastolic on or off hypertensive medication ii. Arterial blood pressure ≤ 140 mmHg systolic and ≤ 90 mmHg diastolic on hypertensive medication c. Hyperlipidemia, meeting at least one of the following criteria: 
 i. Fasting blood total cholesterol level of ≥ 240 mg/dl ii. Fasting total triglyceride level of ≥ 200 mg/dl

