3.4.3. Prior Clinical Experience

A feasibility study (ENDObesity I Study) was conducted in 20 subjects in a single-center study that evaluated the safety and effectiveness of the second generation TPSS. The study included male and female obese subjects, 18 to 55 years of age, with a BMI 35-50 kg/m² or 30-34.9 kg/m² with one or more obesity-related

[figure not shown]
comorbid conditions. The key exclusion criteria included pregnancy, previous gastrointestinal bariatric surgery, GI motility disorder, severe psychiatric conditions, and clinically important comorbid diseases such as insulin-dependent diabetes and uncontrolled hypertension. Subjects with significant endoscopic abnormalities (such as gastroduodenal ulcer, hiatal hernia ≥ 2cm, and erosive esophagitis) were also excluded. Subjects were assigned to two groups of ten subjects. The device residence time was 3 months in first group of 10 subjects and 6 months in the second group of 10 subjects. The primary effectiveness endpoint was percent excess weight loss (EWL). The Impact of Weight on Quality of Life-Lite Questionnaire (IWQOL-Lite) was used to assess patient weight-related quality of life status before and after the treatment.

Subjects were provided nutritional guidelines and encouraged to increase their physical activity at the beginning of the study. No specific dietary or exercise counseling was provided during the study duration after the initial baseline consultation.

The average age of the subjects was 40.7 years ± 10.7 years and 18/20 (90%) were female. The baseline weight was 100.9 kg ± 20.5 kg, with a mean BMI of 36 kg/m² ± 5.5 kg/m² (34.0 kg/m² ± 4.9 kg/m² and 37.9 kg/m² ± 7.3 kg/m² for 3- and 6-month subjects, respectively). Baseline comorbidities included gastroesophageal reflux (50%), osteoarthritis (45%), hypertension (20%), Type 2 diabetes (5%), and sleep apnea (5%).

TPS devices were successfully deployed and removed endoscopically in all subjects with no device or procedure related SAEs peri-procedurally. Mean procedure times were 10.9 minutes ± 3.9 minutes for device deployment (from TPSS insertion to system removal) and 12.9 minutes ± 6.4 minutes for device removal (from overtube insertion to TPS and overtube removal).

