4. STUDY OBJECTIVES

The objective of this study is to demonstrate the safety and effectiveness of the BAROnova TransPyloric Shuttle for weight reduction in patients with BMIs of 30-40 kg/m² compared with the sham-control over the 12 months treatment period.

The study will also assess, as secondary endpoints, changes in weight-related comorbidities, weight-related quality of life, and eating behavior.

The study will be considered a success for efficacy purposes if it meets both of the primary efficacy analyses.

The safety will be characterized, with all adverse events reported. The Clinical Event Committee (CEC) will adjudicate all serious device-related adverse events and any other events deemed necessary.

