15.5.3. Primary Analysis

The %TBL will be calculated as $(\text{Weight}(\text{kg})_{\text{BL}} - \text{Weight}(\text{kg})_{\text{FUP}}) / \text{Weight}(\text{kg})_{\text{BL}}$. Where $\text{Weight}(\text{kg})_{\text{BL}}$ is the subject's weight at baseline in kilograms and $\text{Weight}(\text{kg})_{\text{FUP}}$ is the subject's weight at follow-up in kilograms.

The %TBL will be summarized at each follow-up visit through 12 months along with the observed total body weight at baseline and each follow-up visit by treatment group.

The testing of null hypotheses for the co-primary efficacy endpoints is described in Section 15.3.1.

In order to accommodate missing data in the primary effectiveness analyses, a multiple imputation approach will be used to impute missing follow-up weight observations. A total of 5 imputed samples will be created. Covariates (e.g., gender) will be used in the imputation procedure in addition to the subject's weight from previous visits. The multiple imputation approach was first described by Rubin.³⁵ The SAS procedures MI and MIANALYZE will be used to create the imputations and perform the analysis. The statistical null hypotheses for both co-primary endpoints will be tested on multiply imputed data sets. Sensitivity analyses will be done by evaluating the primary analysis on the ITT and CC cohorts. Further, a last observation carry forward (LOCF) imputation will be performed for the sensitivity purposes.

Additionally, the %TBL median, mean and standard deviation and percent of subjects with greater than 5%TBL will be summarized by treatment group and levels of covariates. Covariates include gender (male versus female), race (Caucasian versus non-Caucasian), age (\leq median, $>$ median), and baseline BMI (30-34.9 kg/m² and 35-40.0 kg/m²).

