15.5.4. Secondary Analysis

Secondary endpoints will be summarized by treatment group for the ITT and per-protocol cohorts based on the observed data and include the following summaries:

- Proportion of subjects achieving at least 7% and 10% TBL at 12 months;
- Percent TBL at 1 week, 1, 2, 4, 6, 9 and 12 months in the Treatment versus Control group;
- Percent EWL at 1 week, 1, 2, 4, 6, 9 and 12 months in the Treatment versus Control group;
- Proportion of subjects who achieve at least one obesity class reduction at 1 week, 1, 2, 4, 6, 9 and 12 months in the Treatment versus Control group;
- Change of BMI at 1 week, 1, 2, 4, 6, 9 and 12 months from baseline in the Treatment versus Control group;
- Change in weight-related quality of life at 1 week, 1, 2, 4, 6, 9 and 12 months as assessed by IWQOL-Lite Questionnaire in the Treatment versus Control group;
- Change in eating behavior at 1 week, 1 month and 12 months as assessed by the Eating Inventory;
- Change in appetite, hunger and fullness at 1 week, 1 month, 6 and 12 months as assessed by Visual Analog Scales in the Treatment versus Control group;
- Change in comorbid conditions and selected clinical parameters at 6 and 12 months in the Treatment group:
 - Prevalence of the metabolic syndrome and its individual components
 - Glucose, insulin, and insulin resistance (as estimated by HOMA)
 - High sensitivity C-reactive protein (hsCRP)
 - Lipid levels (LDL-C, HDL-C, and triglycerides)
 - Blood pressure
 - Waist circumference

The analysis of total body weight loss is described above. The other continuous and binary variables will be summarized descriptively by visit with 95% CIs presented for the mean values and proportions, respectively. For continuous endpoints, the change from baseline will be calculated if appropriate, and a t-test or a sign-rank test used to evaluate the null hypothesis that the change from baseline is centered around 0 (no change) within each treatment group. Treatment group comparisons for continuous endpoints will be made using mixed

models with post-hoc tests for each follow-up, and comparisons for qualitative variables will be made using Fisher's exact test, McNemar test or chi-square test, as appropriate.

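### Section 15.5.4 plans no glucose, blood pressure or lipid analysis in subjects who have the matching condition, and lists these parameters for the Treatment group

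*Combined protocol and SAP*

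**What the plan says.** **Eligibility.** In the Protocol Summary and section 7.2, subjects with BMI 30.0 to 34.9 "are required to have one or more of the following obesity-related mild-moderate comorbidities": type 2 diabetes (2a), hypertension (2b) or hyperlipidaemia (2c). The Patient Population row attaches the condition "with at least one obesity-related comorbidity" to that BMI band only.

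**Aim.** Section 4 says the secondary endpoints will assess "changes in weight-related comorbidities, weight-related quality of life, and eating behavior".

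**Analysis.** Section 15.5.4 opens: "Secondary endpoints will be summarized by treatment group for the ITT and per-protocol cohorts based on the observed data". Its comorbidity item reads "Change in comorbid conditions and selected clinical parameters at 6 and 12 months in the Treatment group" and covers metabolic syndrome and its components, glucose, insulin, HOMA, hsCRP, lipids, blood pressure and waist. Sections 1 and 6.2 also list these for the Treatment group, whereas several neighbouring items name both arms. For continuous endpoints the plan has "a t-test or a sign-rank test used to evaluate the null hypothesis that the change from baseline is centered around 0", within each arm. A later general sentence adds mixed-model comparisons between treatment groups and does not say whether it includes the comorbidity items.

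**Subgroups.** Section 15.5.3 plans summaries of %TBL and of the 5% responder rate by covariate: "Covariates include gender (male versus female), race (Caucasian versus non-Caucasian), age" and baseline BMI. No comorbidity is on the list.

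**Status.** Section 15.1 makes secondary results an aid to interpretation that is not needed for study success.

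**The concern.** A subject without hypertension contributes to the blood pressure mean, and a subject without diabetes to the glucose mean. If such subjects change less, a modest overall change could hide a useful improvement in those with the condition, or could come mainly from subjects in the normal range. The visible plan has no analysis that tells these apart.

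The second weakness is the comparison. Both arms receive the same counselling (section 5.1). Section 15.4 assumes that Control subjects lose 5% of body weight, and section 2.2 says that a loss as small as 3% can improve some cardiovascular risk factors. On the plan's own assumptions, then, a non-zero change within the Treatment arm may be expected even if the device adds nothing. Subjects who entered because a value was high will also tend to drift down on re-measurement.

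What is at stake is how the comorbidity results can be read against the section 4 aim. Study success does not depend on it.

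**Working it through.** **1. The plan's own figures.** Section 15.4 gives no power for the comorbidity endpoints. Its evaluable numbers, 162 versus 81, are used below, so its calculation is checked first. With SD 9, SE = 9 × sqrt(1/162 + 1/81) = 9 × 0.1361 = 1.225.
- Margin 4: (8 − 4)/1.225 = 3.27, power = Φ(3.27 − 1.96) = 90% (stated 90%).
- Margin 5: (8 − 5)/1.225 = 2.45, power = Φ(2.45 − 1.96) = 69%, or 68.4% with the noncentral t (stated 68.4%).

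Both reproduce.

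**2. Inputs for the dilution.** Let f be the share with the condition and r the effect in unaffected subjects divided by the effect in affected subjects. The documents give neither for this cohort. Section 3.4.3 reports hypertension in 20% and type 2 diabetes in 5% of 20 feasibility subjects, and lists no hyperlipidaemia. Eligibility differed there, and here a comorbidity is compulsory at BMI 30.0 to 34.9. So f and r are assumptions and are shown as ranges. The effect in affected subjects, d = 0.5 SD, is also an assumption.

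**3. Formulas** (equal SD, same f in both arms):
- Whole-group mean as a share of the affected-subject effect: w = f + (1 − f)r
- z, whole group: w × d / 0.1361
- z, affected subset: d × sqrt(f) / 0.1361
- The subset is the stronger test only if w < sqrt(f), that is, r < sqrt(f)/(1 + sqrt(f)). The sample size and d cancel.

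**4. Example, f = 20%.** Subset z = 0.5 × 0.447/0.1361 = 1.64, two-sided power 38%. Whole group at r = 0: w = 0.20, z = 0.73, power 11%. At r = 0.5: w = 0.60, z = 2.20, power 60%. Break-even r = 0.447/1.447 = 0.31.

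**5. Results, 162 versus 81, two-sided 5%, both tails counted.**

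| f | Affected, T / C | w at r = 0, 0.25, 0.5 | Subset power | Whole-group power at r = 0, 0.25, 0.5 | Break-even r |
|---|---|---|---|---|---|
| 5% | 8 / 4 | 0.05, 0.29, 0.53 | 13% | 5%, 18%, 49% | 0.18 |
| 20% | 32 / 16 | 0.20, 0.40, 0.60 | 38% | 11%, 31%, 60% | 0.31 |
| 30% | 49 / 24 | 0.30, 0.48, 0.65 | 52% | 20%, 42%, 67% | 0.35 |
| 50% | 81 / 40 | 0.50, 0.63, 0.75 | 74% | 45%, 63%, 79% | 0.41 |

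The mean is diluted whenever r is below 1. Power is lost only when r is below the last column. At r = 0.5 the whole group is the stronger test in every row.

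**6. Precision of the subset.** The half-width of the 95% CI is 1.96 × 0.1361/sqrt(f) SD: 0.60 SD at 20%, 0.49 at 30%, 0.38 at 50% and 1.19 at 5%, against 0.27 SD for the whole group.

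**The case against.** **Unaffected subjects may also improve.** The documents' definitions make r = 0 unlikely. An unmedicated subject at 135/88 mmHg fails definition 2b but meets the blood pressure component of metabolic syndrome (130/85, Appendix A). Triglycerides show the same gap (200 versus 150 mg/dl). This stands. A reader might infer that any effect on these conditions is diluted and that the whole-group analysis must lose power. The documents supply neither r nor f, and the table shows the opposite at r = 0.5.

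**Metabolic syndrome components already address status.** They are listed, and McNemar's test, if used for within-arm change, rests only on subjects whose status changes. This stands in part. The component cut-offs differ from 2a to 2c, LDL is not a component, drug therapy counts as meeting the glucose, blood pressure, triglyceride and HDL components, and the stated listing is still for the Treatment group.

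**The subset is imperfect too.** Definitions 2a(ii), 2b(ii) and 2c(iv) admit treated or controlled subjects with little room to improve. Sections 3.5.5 and 10.3.2 foresee medication reductions, so benefit could appear as less medication with unchanged values. This stands, and is why medication change must be reported alongside.

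**It is only supportive.** Correct under section 15.1. Section 15.5.7 is also redacted, so a relevant plan there cannot be ruled out.

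**Conclusion.** The point holds as a gap in interpretation. The visible plan has no analysis of glucose, insulin/HOMA, blood pressure or lipids in subjects with the matching condition, and leaves open whether these parameters are compared with Control. That no restriction applies is inferred from the absence of one in section 15.5.4.

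The size of the dilution cannot be determined for this trial. Under equal SD, restricting to affected subjects gains power only if unaffected subjects have less than about 31%, 35% or 41% of the effect (20%, 30% or 50% affected). If the pivotal cohort resembled the feasibility study's 5% with diabetes, that subset would be about 12 evaluable subjects and descriptive only. hsCRP, waist and metabolic syndrome prevalence do not belong to one eligibility condition and are not part of the point.

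A reader might go further and conclude that the comorbidity results will be uninformative, or that the trial's conclusions are at risk. The documents do not support that: the whole-group summaries remain legitimate, and the co-primary endpoints, sample size and alpha are untouched.

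**What to change.** In section 15.5.4:

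1. Keep the existing whole-group summaries, including hsCRP, waist and metabolic syndrome prevalence.
2. State that the comorbidity parameters are compared Treatment versus Control, and reconcile the Treatment-group listing in sections 1, 6.2 and 15.5.4 with the general sentence on treatment group comparisons.
3. Add Treatment versus Control differences with 95% CI at 6 and 12 months, labelled supportive: glucose, insulin and HOMA in subjects meeting 2a; blood pressure in those meeting 2b; lipids in those meeting 2c. Classify every subject from data recorded before the index procedure, whatever the BMI.
4. Report changes in the relevant medication by arm beside each table.
5. Base any conclusion on the between-arm difference, since regression to the mean is expected in both arms.

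The cost is SAP text and three sets of tables. Laboratory values, blood pressure and medications are already collected before the procedure and at 6 and 12 months (sections 11.4 and 11.9). The price is wide intervals and more secondary estimates: eight parameters (glucose, insulin, HOMA, systolic and diastolic pressure, LDL-C, HDL-C, triglycerides) × 2 visits = 16 per population, 32 for ITT and PP. Randomisation is stratified by center only (section 5.3), so small subsets may be unbalanced by chance. The additions should be fixed before unblinding.

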2. BACKGROUND

Obesity is a major public health issue in the United States with 78 million adults now obese. In 2009-2010, the prevalence of obesity in the US was 35.5% among men and 35.8% among women.¹ The annual healthcare costs associated with obesity have been estimated at up to 8% of overall healthcare budgets. Recognizing the health consequence and the morbidity and mortality associated with obesity, the American Medical Association officially classified obesity as a disease in 2013.²

2.1. Definition of Obesity

Obesity is defined as a body mass index (BMI) that exceeds 30 kg/m². A BMI of 18.5-25 kg/m² is defined as normal and 25-30 kg/m² as overweight. Obesity is further classified into three groups: moderate (Class I, BMI 30.0 – 34.9), severe (Class II, BMI 35.0 – 39.9), and very severe (Class III, BMI > 40).³

2.2. Obesity Related Comorbidities and the Benefit of Modest Weight Loss

Substantial evidence suggests that obesity is associated with significant morbidity and mortality. A comprehensive systematic review and meta-analysis including 87 high quality prospective cohort studies concluded that excess body weight was associated with the incidence of multiple comorbidities, including Type 2 diabetes mellitus, cardiovascular diseases, cancers, asthma, osteoarthritis and gallbladder disease.⁴ A BMI \geq 30 kg/m² is also associated with reduced life expectancy.^{5,6}

Weight loss has been shown to improve many of the comorbidities associated with obesity and results in significant improvements in components of the metabolic syndrome.^{7,8,9} A weight loss as small as 3% can result in improvements in some cardiovascular disease risk factors and a weight loss of 5% or more is generally considered to be clinically meaningful.^{10,11} A loss of 5% to 10% of body weight is associated with decreased cardiovascular disease risk factors, prevention or delay of the development of Type 2 diabetes, and improvement of other health consequences of obesity.^{12,13} Greater weight loss produces greater reductions in cardio metabolic risk.¹⁴ The recently published 2013 AHA/AAC/TOS Guideline recommends a chronic disease management model for obesity, in which patients are encouraged to lose 5% to 10% of their body weight as an initial goal to decrease the risk of the development, or amelioration of, obesity-related medical conditions and cardiovascular risk factors.¹⁵

2.3. Treatment Options

2.3.1. Lifestyle Modification Interventions

Lifestyle modification focuses on caloric reduction, increased physical activity, and behavioral modification strategies. Lifestyle intervention by itself results in moderate weight loss. Although studies performed in academic centers have shown that intensive lifestyle modification delivered in weekly counseling sessions can produce a 7-10% weight loss and improvements in weight-related health problems within 6 months, the “real world” outcomes are often more modest and are largely influenced by the delivery methods, intensity, and duration of the interventions. A recent example of this is the POWER-UP study which randomized 390 subjects into three types of intervention: usual care, consisting of quarterly primary care provider (PCP) visits that included education about weight management; brief lifestyle counseling, consisting of quarterly PCP visits combined with brief monthly sessions with lifestyle coaches who instructed participants about behavioral weight control; or enhanced brief lifestyle counseling, which also provided quarterly physician visits and monthly lifestyle counseling sessions but included the use of meal replacement products or weight-loss medication. The change in body weight (% TBL) with usual care, brief lifestyle counseling, and enhanced

brief lifestyle counseling was $2.1\% \pm 0.6\%$, $3.5\% \pm 0.6\%$, and $7.0\% \pm 0.6\%$ at 1 year ($P < 0.001$), and $1.6\% \pm 0.6\%$, $2.9\% \pm 0.7\%$, and $4.7\% \pm 0.6\%$ ($P < 0.001$) at 2 years, respectively.¹⁶

Outcomes of lifestyle modification interventions are greatly influenced by patient motivation as well as adherence and compliance over time. It is, however, important to recognize that lifestyle modification is an essential component of any weight loss intervention, including pharmacotherapy and bariatric surgery.

